Platelets, decreased	100,000 – 124,999/mm ³ $100,000 \times 10^9$ – $124,999 \times 10^9/L$	50,000 – 99,999/mm ³ $50,000 \times 10^9$ – $99,999 \times 10^9/L$	25,000 – 49,999/mm ³ $25,000 \times 10^9$ – $49,999 \times 10^9/L$	< 25,000/mm ³ $< 25,000 \times 10^9/L$
WBC, decreased	2,000 – 2,500/mm ³ $2,000 \times 10^9$ – $2,500 \times 10^9/L$	1,500 – 1,999/mm ³ $1,500 \times 10^9$ – $1,999 \times 10^9/L$	1,000 – 1,499/mm ³ $1,000 \times 10^9$ – $1,499 \times 10^9/L$	< 1,000/mm ³ $< 1,000 \times 10^9/L$

LABORATORY				
PARAMETER	GRADE 1 MILD	GRADE 2 MODERATE	GRADE 3 SEVERE	GRADE 4 POTENTIALLY LIFE-THREATENING
CHEMISTRIES Standard International Units are listed in italics				
Acidosis	NA	pH < normal, but \geq 7.3	pH < 7.3 without life-threatening <small>consequences</small>	pH < 7.3 with life-threatening <small>consequences</small>
Albumin, serum, low	3.0 g/dL – < LLN 30 g/L – < LLN	2.0 – 2.9 g/dL 20 – 29 g/L	< 2.0 g/dL < 20 g/L	NA
Alkaline Phosphatase	1.25 – 2.5 x ULN [†]	2.6 – 5.0 x ULN [†]	5.1 – 10.0 x ULN [†]	> 10.0 x ULN [†]
Alkalosis	NA	pH > normal, but \leq 7.5	pH > 7.5 without life-threatening <small>consequences</small>	pH > 7.5 with life-threatening <small>consequences</small>
ALT (SGPT)	1.25 – 2.5 x ULN	2.6 – 5.0 x ULN	5.1 – 10.0 x ULN	> 10.0 x ULN
AST (SGOT)	1.25 – 2.5 x ULN	2.6 – 5.0 x ULN	5.1 – 10.0 x ULN	> 10.0 x ULN
Bicarbonate, serum, low	16.0 mEq/L – < LLN 16.0 mmol/L – < LLN	11.0 – 15.9 mEq/L 11.0 – 15.9 mmol/L	8.0 – 10.9 mEq/L 8.0 – 10.9 mmol/L	< 8.0 mEq/L < 8.0 mmol/L
Comment: Some laboratories will report this value as Bicarbonate (HCO ₃) and others as Total Carbon Dioxide (CO ₂). These are the same tests; values should be graded according to the ranges for Bicarbonate as listed				
Bilirubin (Total)				
Adult and Pediatric > 14 days	1.1 – 1.5 x ULN	1.6 – 2.5 x ULN	2.6 – 5.0 x ULN	> 5.0 x ULN
Calcium, serum, high				
Adult and Pediatric \geq 7 days	10.6 – 11.5 mg/dL 2.65 – 2.88 mmol/L	11.6 – 12.5 mg/dL 2.89 – 3.13 mmol/L	12.6 – 13.5 mg/dL 3.14 – 3.38 mmol/L	> 13.5 mg/dL > 3.38 mmol/L
Calcium, serum, low				
Adult and Pediatric \geq 7 days	7.8 – 8.4 mg/dL 1.95 – 2.10 mmol/L	7.0 – 7.7 mg/dL 1.75 – 1.94 mmol/L	6.1 – 6.9 mg/dL 1.53 – 1.74 mmol/L	< 6.1 mg/dL < 1.53 mmol/L
Comment: Do not adjust Calcium, serum, low or Calcium, serum, high for albumin				

LABORATORY				
PARAMETER	GRADE 1 MILD	GRADE 2 MODERATE	GRADE 3 SEVERE	GRADE 4 POTENTIALLY LIFE-THREATENING
Cardiac troponin I (cTnI)	NA	NA	NA	Levels consistent with myocardial infarction or unstable angina as
Cardiac troponin T (cTnT)	NA	NA	NA	≥ 0.20 ng/mL OR Levels consistent with myocardial infarction or unstable angina as
Cholesterol (fasting)				
Adult ≥ 18 years	200 – 239 mg/dL 5.18 – 6.19 mmol/L	240 – 300 mg/dL 6.20 – 7.77 mmol/L	> 300 mg/dL > 7.77 mmol/L	NA
Creatine Kinase	$3.0 – 5.9 \times ULN^{\dagger}$	$6.0 – 9.9 \times ULN^{\dagger}$	$10.0 – 19.9 \times ULN^{\dagger}$	$\geq 20.0 \times ULN^{\dagger}$
Creatinine	$1.1 – 1.3 \times ULN^{\dagger}$	$1.4 – 1.8 \times ULN^{\dagger}$	$1.9 – 3.4 \times ULN^{\dagger}$	$\geq 3.5 \times ULN^{\dagger}$

LABORATORY				
PARAMETER	GRADE 1 MILD	GRADE 2 MODERATE	GRADE 3 SEVERE	GRADE 4 POTENTIALLY LIFE-THREATENING
Glucose, serum, high				
Nonfasting	116 – 160 mg/dL 6.44 – 8.88 mmol/L	161 – 250 mg/dL 8.89 – 13.88 mmol/L	251 – 500 mg/dL 13.89 – 27.75	> 500 mg/dL > 27.75 mmol/L
Fasting	110 – 125 mg/dL 6.11 – 6.94 mmol/L	126 – 250 mg/dL 6.95 – 13.88 mmol/L	251 – 500 mg/dL 13.89 – 27.75	> 500 mg/dL > 27.75 mmol/L
Glucose, serum, low				
Adult and Pediatric ≥ 1 month	55 – 64 mg/dL 3.05 – 3.55 mmol/L	40 – 54 mg/dL 2.22 – 3.06 mmol/L	30 – 39 mg/dL 1.67 – 2.23 mmol/L	< 30 mg/dL < 1.67 mmol/L
Lactate	ULN - < 2.0 x ULN without acidosis	≥ 2.0 x ULN without acidosis	Increased lactate with pH < 7.3 without life- threatening	Increased lactate with pH < 7.3 with life- threatening
Comment: Added ULN to Grade 1 parameter				
LDL cholesterol (fasting)				
Adult ≥ 18 years	130 – 159 mg/dL 3.37 – 4.12 mmol/L	160 – 190 mg/dL 4.13 – 4.90 mmol/L	≥ 190 mg/dL ≥ 4.91 mmol/L	NA
Lipase	1.1 – 1.5 x ULN	1.6 – 3.0 x ULN	3.1 – 5.0 x ULN	> 5.0 x ULN
Magnesium, serum, low	1.2 – 1.4 mEq/L 0.60 – 0.70 mmol/L	0.9 – 1.1 mEq/L 0.45 – 0.59 mmol/L	0.6 – 0.8 mEq/L 0.30 – 0.44 mmol/L	< 0.60 mEq/L < 0.20 mmol/L
Pancreatic amylase	1.1 – 1.5 x ULN	1.6 – 2.0 x ULN	2.1 – 5.0 x ULN	> 5.0 x ULN
Phosphate, serum, low				
Adult and Pediatric ≥ 14 years	2.5 mg/dL - < LLN 0.81 mmol/L - < LLN	2.0 – 2.4 mg/dL 0.65 – 0.80 mmol/L	1.0 – 1.9 mg/dL 0.32 – 0.64 mmol/L	< 1.00 mg/dL < 0.32 mmol/L
Potassium, serum, high	5.6 – 6.0 mEq/L 5.6 – 6.0 mmol/L	6.1 – 6.5 mEq/L 6.1 – 6.5 mmol/L	6.6 – 7.0 mEq/L 6.6 – 7.0 mmol/L	> 7.0 mEq/L > 7.0 mmol/L
Potassium, serum, low	3.0 – 3.4 mEq/L 3.0 – 3.4 mmol/L	2.5 – 2.9 mEq/L 2.5 – 2.9 mmol/L	2.0 – 2.4 mEq/L 2.0 – 2.4 mmol/L	< 2.0 mEq/L < 2.0 mmol/L
Sodium, serum, high	146 – 150 mEq/L 146 – 150 mmol/L	151 – 154 mEq/L 151 – 154 mmol/L	155 – 159 mEq/L 155 – 159 mmol/L	≥ 160 mEq/L ≥ 160 mmol/L
Sodium, serum, low	130 – 135 mEq/L 130 – 135 mmol/L	125 – 129 mEq/L 125 – 129 mmol/L	121 – 124 mEq/L 121 – 124 mmol/L	≤ 120 mEq/L ≤ 120 mmol/L
Triglycerides (fasting)	NA	500 – 750 mg/dL 5.65 – 8.48 mmol/L	751 – 1,200 mg/dL 8.49 – 13.56 mmol/L	> 1,200 mg/dL > 13.56 mmol/L

LABORATORY				
PARAMETER	GRADE 1 MILD	GRADE 2 MODERATE	GRADE 3 SEVERE	GRADE 4 POTENTIALLY LIFE-THREATENING
Uric acid	7.5 – 10.0 mg/dL 0.45 – 0.59 mmol/L	10.1 – 12.0 mg/dL 0.60 – 0.71 mmol/L	12.1 – 15.0 mg/dL 0.72 – 0.89 mmol/L	> 15.0 mg/dL > 0.89 mmol/L
URINALYSIS Standard International Units are listed in italics				
Hematuria (microscopic)	6 – 10 RBC/HPF	> 10 RBC/HPF	Gross, with or without clots OR with RBC casts	Transfusion indicated
Proteinuria, random collection	1 +	2 – 3 +	4 +	NA
Proteinuria, 24 hour collection				
Adult and Pediatric ≥ 10 years	200 – 999 mg/24 h 0.200 – 0.999 g/d	1,000 – 1,999 mg/24 h	2,000 – 3,500 mg/24 h	> 3,500 mg/24 h > 3.500 g/d

Appendix 5.

Fecal Microbiota Transplantation - Record of Side Effects

This diary is one way researchers will get information from you regarding any possible problems or side effects in this study.

- ❖ **What you are going to do is simple.** Just keep a record of any unpleasant thing that happens to you while you are in the study, before, during, and after we have completed the stool transplant. We even want you to record things that do not seem to be part of the stool therapy, at all.
- ❖ **When do you start? When do you end?** You will record one entry 1-week prior and on the day of the transplant. You will then complete one entry per day for the first week following the treatment and then once a week thereafter for 12-weeks.
- ❖ **What do you look for? What do you report?** Any symptom or problem whether or not it may be from the medicine, stool therapy. This could include: fever, abdominal pain, a big belly, lots of gas, diarrhea, nosebleeds, and anything else you know is not quite right.
- ❖ **What will you do?** In the first 7 days after the transplant, you will report some of the specific things that have bothered you by checking the boxes in the diary (see below). You can also write any other problems that you may have had during that time. **Additionally, you will record your temperature once for each day for the first 7 days after the transplant, unless you feel hot. If you feel hot, please take your temperature again.**
Please make sure to record the highest temperature taken that day if you take it more than once.

Continue to record any problem up to 6 months after the transplant.

How will you record it? Like this...

EVENT	DATE OF ONSET	INTENSITY	ACTION TAKEN	MEDICATION	DATE RESOLVED
Fever	3/1/12	3	Missed 2 days of school	Tylenol-200mg	3/3/12
Sore throat	3/5/12	1	None	None	3/6/12

OTHER SYMPTOMS

Record each symptom at its **worst** level for each day.

For example, a sore throat that starts at 'Grade 1' but increases to 'Grade 2' should be recorded as 'Grade 2'.

Examples of Grades:

Grade 1 – Mild: I noticed the symptom. It did not keep me from doing my normal activities.

Grade 2 – Moderate: I noticed the symptom and it kept me from doing some of my normal activities.

Grade 3 – Severe: I really noticed the symptom and it kept me from doing activities that I wanted or needed to do.

Grade 4 – Very severe: The symptom made me unable to perform basic self-care functions such as washing myself **OR** medical or surgical intervention was needed to prevent serious consequences.

Subject ID: _____

Date: ____ / ____ / ____

Check here if no side effects present:

Highest temperature of the day: _____ °F

Total Number of Stools: _____

Check if symptom present	Event	Date of Onset	Intensity	Action taken	Medications	Date Resolved
	Fever					
	Abdominal Pain/					
	Diarrhea					
	Nausea/Vomiting					
	Blood in Stool					
	Other 1					
	Other 2					
	Other 3					

Grade 1 – Mild: I noticed the symptom. It did not keep me from doing my normal activities.

Grade 2 – Moderate: I noticed the symptom and it kept me from doing some of my normal activities.

Grade 3 – Severe: I really noticed the symptom and it kept me from doing activities that I wanted or needed to do.

Grade 4 – Very severe: The symptom made me unable to perform basic self-care functions such as washing myself **OR** medical or surgical intervention was needed to prevent serious consequences.

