Hypothesis: Fecal microbiota transplantation will result in a sustained repopulation of the patient's microbiome that corresponds to the bacteria from the donor stool.

III. Methods and Study Design

This is a randomized controlled pilot study to assess the safety and to measure the microbiological and clinical impacts of FMT in patients with obesity. We will continue to prospectively enroll and screen adult patients until 20 patients have completed all study visits. We anticipate total enrollment to be 50 patients to account for screen fails and dropouts. Eligible patients are those who are obese (BMI of 35 kg/m² or greater). Patients will be randomized 1:1 to receive FMT or placebo. The participants will receive either an FMT from a lean healthy donor using 30 induction FMT capsules or placebo capsules. The participants will continue to receive a monthly maintenance dose of 12 FMT oral capsules or placebo at week 4 and week 8. Serum for hormone levels will be collected at baseline, weeks 1, 4, 6, 8 and 12. Stool for microbial assessment will be collected at baseline and weeks 1, 4, 6, 8, 12, 26, and 52. A Food Frequency Questionnaire will be taken by the patient at week 0. Donor Stool will be obtained from OpenBiome. OpenBiome is a nonprofit 501(c)(3) organization that provides hospitals with screened, filtered, and frozen material ready for clinical use (See Attachments for OpenBiome Quality and Safety Program as well as donor screening examples).

Primary Safety Endpoint:

Safety Endpoints: Number and nature of adverse events at week 1, 6, 12 and 26.

Primary Clinical Endpoint:

The primary clinical end point is an increase in the AUC for GLP-1 after a mixed meal test from baseline and 12.

Secondary Endpoints:

- Microbial Endpoints: Recipients fecal microbial diversity at week 6 and 12 compared to baseline
- Clinical Endpoints: Decrease in BMI and waste circumference at week 6 and 12 compared to baseline.

Trial Treatment:

The treatment for this trial will be administration of an induction dose of 30 FMT capsules ingested orally. Treatment will occur after screening.

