This is an exploratory study as relatively little is known about the microbiome of patients with obesity. Thus, the main objective of our study is to assess the safety of FMT in obese patients. Secondarily we will be able to characterize variability in the microbiome of obese patients to aid

in estimating effect sizes for designing larger studies powered to detect associations between microbiome data and GLP-1 levels and possible weight loss/BMI.

**IX. Risks and Discomforts:
Fecal Microbial Therapy:**

Known Risks of FMT

- Altered bowel pattern (diarrhea, constipation)
- Cramping
- Belching

Potential Risks of FMT

- Transmission of pathogenic bacteria, viruses, fungi
- Transmission of allergens
- Alteration in intestinal metabolism

Privacy and Confidentiality:

This study involves the collection of personal health information. Accidental release of personal health information is a risk of participation in this study. Measures will be taken to protect the confidentiality of all subjects' information. These measures include keeping all information collected about the subjects' confidential, keeping information in locked rooms, and having physicians who are directly involved with a subject's clinical care involved in the study.

Venipuncture: Risks of having blood drawn include pain, bruising, or infection.

Pregnancy: The risks to fetuses and women who are pregnant are unknown.

X. Potential Benefits:

Subjects may not receive any benefits from taking part in this study. However this research and the results of this study may benefit others in the future.

The potential benefits include:

- Restoration of fecal diversity
- Increase in GLP-1 hormones
- Weight loss

[figure not shown]
As this is a pilot study, it is difficult to quantify the expected benefits.

XI. Monitoring and Quality Assurance:

The Principal Investigator, [name], will assure the validity and integrity of the data and adherence to the IRB-approved protocol.

Study staff will review completed CRF's before each visit to ensure completeness of previous entries. Entries that need clarification will be reviewed by the PI, and the subject and/or treating gastroenterologist will be consulted if needed.

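### The symptom diary has no named row for constipation or belching, two of the four symptoms the protocol lists as known FMT risks, so these may be recorded less completely than the symptoms it prompts for

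*Combined protocol and SAP*

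**What the plan says.** Five places bear on this point.

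- **Section III, Primary Safety Endpoint.** The endpoint is "Number and nature of adverse events at week 1, 6, 12 and 26". It counts adverse events from any source, not diary ticks.
- **Section IX, known risks of FMT.** The list opens with "Altered bowel pattern (diarrhea, constipation" and continues with cramping and belching. It gives no frequencies and no ranking.
- **Appendix 5, instructions.** For the first seven days, "you will report some of the specific things that have bothered you by checking the boxes in the diary". The next sentence adds: "You can also write any other problems that you may have had during that time". The prompt for what to look for reads: "This could include: fever, abdominal pain, a big belly, lots of gas, diarrhea, nosebleeds, and anything else you know is not quite right".
- **Appendix 5, card.** The named rows are fever, "Abdominal Pain" (the label continues after a slash and is cut off in the available text), diarrhea, "Nausea/Vomiting" and blood in stool, followed by three blank rows. The card also has a field for "Total Number of Stools" and a box to tick if there were no side effects.
- **Sections III, IV and VII, other collection.** There is a call four hours after each ingestion visit, direct interviews at weeks 1, 4, 6, 8 and 12, and telephone assessments at weeks 26 and 52. Section VII describes the diary as an aid to the patient's memory that the principal investigator reviews. Section IV has it completed weekly over weeks 2 to 12 to monitor adverse events.

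**The concern.** Symptoms that a form names and symptoms that the patient must think to write in are not collected in the same way, and the second kind tends to be reported less often when mild. Here the line between the two cuts through the protocol's own list of known product effects: diarrhea gets a box, while constipation and belching do not.

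Safety is the trial's stated main objective, and Aim 1 hypothesizes that FMT is safe and well tolerated. If mild constipation and belching are captured less fully, their recorded rates will be too low and any absolute excess over placebo will look smaller. That is the direction that favors the hypothesis. A larger trial planned from these rates would inherit the gap.

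**Working it through.** **Step 1: compare the known risks with the card.** The documents state no adverse event rate, so there is no figure of the plan's own to reproduce.

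| Known risk (Section IX) | Named row on card | Other prompt in Appendix 5 |
|---|---|---|
| Diarrhea | Yes | Named in instructions; stool count |
| Cramping | Plausibly, under the abdominal pain row (label cut off) | Abdominal pain named in instructions |
| Constipation | No | Stool count, indirectly |
| Belching | No | Gas named in instructions, not belching |

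Two of the four have no named row in the available text.

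**Step 2: see what the other routes add.**

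- *Interviews* take place in weeks 1, 4, 6, 8 and 12. In the other seven of the first 12 weeks (2, 3, 5, 7, 9, 10, 11) the weekly card is the only scheduled collection. No script or checklist naming the two symptoms appears in the text.
- *The four-hour call* comes too soon to show constipation caused by that dose.
- *The stool count* sits on a card with one date. After the first week the cards are weekly, so the count may cover one day in seven. It says nothing about belching.
- *Grading (Appendix 4)* gives constipation its own row but marks Grade 1 as not applicable, so mild constipation lacks a specific grade as well as a box.

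These routes reduce the gap, but none is stated to close it.

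**Step 3: illustrate the size, on assumed inputs.** From the documents: 20 completers randomized 1:1, so about 10 on FMT. Assumed: a true rate *p* and a share *s* of cases that reach the record by any route.

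P(at least one recorded) = 1 − (1 − p·s)^10

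| True rate p | s = 1.00 | s = 0.75 | s = 0.50 |
|---|---|---|---|
| 10% | 65% | 54% | 40% |
| 20% | 89% | 80% | 65% |
| 30% | 97% | 92% | 80% |

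For example, at p = 0.2: 1 − 0.80^10 = 0.893, 1 − 0.85^10 = 0.803, 1 − 0.90^10 = 0.651.

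**Step 4: allow for a second route.** Assume a box catches 90% of cases and a blank row 50%, with p = 0.2.

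- *Card alone:* P(no report) is (1 − 0.18)^10 = 0.137 with a box and (1 − 0.10)^10 = 0.349 without, a gap of about 21 points.
- *Interviews also catch 50%, independently:* capture is 1 − 0.1 × 0.5 = 0.95 with a box and 1 − 0.5 × 0.5 = 0.75 without. P(no report) is (1 − 0.19)^10 = 0.122 and (1 − 0.15)^10 = 0.197, a gap of about 8 points.

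**Step 5: effect on the comparison with placebo.** If capture is equal in both arms, the observed difference is s × (p_FMT − p_placebo). With assumed true rates of 40% and 10%, 90% capture shows 36% against 9% (27 points) and 50% capture shows 20% against 5% (15 points). The ratio stays at 4 in both cases; only the absolute difference shrinks.

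**The case against.** The strongest reply is that the diary is not the endpoint. The endpoint is all adverse events. The diary is a memory aid, and its patient text presents it as one source among others. Patients are told to record anything unpleasant, whether or not it seems related, and the write-in instruction directly follows the tick-box sentence. Gas is prompted by name, which comes close to belching. Interviews and calls come on top. Both masked arms follow the same procedures, so a gap in the card does not clearly favor either arm. This is also an exploratory pilot with no stated formal safety test.

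Most of this stands, and it limits the conclusion. A reader might infer that the primary safety endpoint does under-record the events the trial most expects, and that a low constipation rate or a small difference from placebo would be an artefact of the form. The documents do not support that. Under-recording is a risk, not a shown result. Section IX ranks nothing, diarrhea has a box, and cramping is plausibly covered. Equal under-capture scales an absolute difference down but does not by itself create a small one.

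What the reply does not remove is the uneven prompting. Being allowed to write a symptom in is weaker than being asked about it, and the text gives no assurance that interviewers ask.

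**Conclusion.** The gap in the form is certain on the available text: two of the four known symptoms have no named row, and no interview is said to ask about them by name. It is reasonable, but not demonstrated, that mild constipation and belching would be recorded less completely than the prompted symptoms. If so, absolute rates would be too low in both arms and any absolute difference from placebo would shrink.

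The size cannot be derived. The figures in the working rest on assumed event rates, assumed capture shares, independence of card and interview, and equal capture in both arms. They show only that the effect could range from modest to material with 10 patients per arm. One caveat on the text: the abdominal pain label is cut off and may name a further symptom. This is a worthwhile, inexpensive improvement to safety collection, not a flaw that invalidates the endpoint.

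**What to change.** Add two tick rows to the Appendix 5 card, *Constipation* and *Belching/gas*, and use that card in both arms at every card date, including baseline, so that new symptoms can be told from pre-existing ones. State in Sections IV and VII that the scheduled adverse event interviews and calls ask about the same symptoms by name. No change to the abdominal pain row is proposed, because its full label cannot be seen.

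The cost is a revised one-page form, a sentence or two of protocol text and IRB notification. The downside is that slightly more mild events will be recorded in both arms. If patients have already used the present card, record which version each one completed, because rates before and after the change will not be comparable.

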Appendix 6.

Sensormedics Vmax Encore 29(VIASYS Respiratory Care Inc., Yorba Linda, CA)

Indirect Calorimetry Measurements information use in protocols.

During a metabolic study we are measuring Resting Energy Expenditure (REE) or the number of calories being burned at rest per day. Depending on body size, a healthy adult may burn from 1000 to 3000 Kcal per day just to maintain normal body functions. Traditionally, predicted equations were used to estimate REE based on age, height, and weight. Unfortunately these equations do not account for stress factors that could be affecting the patient (fever, burns, disease, medications, etc.).

Indirect Calorimetry calculates heat production by measuring gas exchange; in other words, oxygen consumption and carbon dioxide production. During resting conditions food sources are broken down to produce energy (heat or KCALS). The oxygen consumed and the carbon dioxide produced are measured to provide an indirect assessment of caloric expenditure. REE provides the total energy expenditure in 24 hours and is calculated from the gas exchange data (VO₂, VCO₂) collected by the Vmax. The parameter RQ will assist in determining subject's caloric needs. RQ provides information on what the subject is utilizing for energy; carbohydrates, fats, or proteins.

$$RQ = VCO_2/VO_2$$

Carbohydrates .90 - 1.00

Fats .70 - .78

Proteins .80

Combination Fats/Carbohydrates .80 - .82

RQ greater than 1.00 – 1.20 may indicate overfeeding (Lipogenesis)

RQ less than .70 may indicate underfeeding (Ketogenesis)

NOTE: Hyperventilation can cause the RQ to exceed 1.00

Testing Procedure:

Energy expenditure (EE), respiratory quotient (RQ) and substrate utilization will be calculated from measurements of oxygen (VO₂) and carbon dioxide (VCO₂) in inspired and expired air. The fasted subject (12 hours prior to testing) is placed in a supine position in a quiet environment where subject will be undisturbed. Subject is also fully rested and has not performed an exercise prior to testing. The Sensormedics Vmax Encore equipment

(VIASYS Respiratory Care Inc., Yorba Linda, CA) is used to collect measurements at specified study times.

